8.4 Missing Data

After signing the informed consent, patients still are allowed to withdraw from the study. Every attempt will be made to collect the primary end-point. Withdrawal by the investigator will mainly be because of safety reasons and mostly constitute a treatment failure.

The statistical analyst will consider all possible reasons for missing data. If it is safe to assume that the data are missing at random (MAR) or missing completely at random (MCAR) we will use multiple imputation for missing values.

Sensitivity analyses will be used to investigate the validity of the MAR assumption against missing not at random (MNAR).

8.5 Interim Analyses and Data Monitoring (as applicable)

An interim analysis will be performed at 50% of patient accrual, analysing the primary outcome and safety data. The safety data consists of observed adverse events and SAE. A DSMB will assess this interim analysis. The advice(s) of the DSMB will only be sent to the principal investigator of the study. Should the principal investigator decide not to fully implement the advice of the DSMB, the

principal investigator will send the advice to the reviewing Ethical Committee (in Dutch: METC), including a note to substantiate why (part of) the advice of the DSMB will not be followed.

Criteria on which the DSMB may decide to terminate the trial prematurely are:

1. Any serious adverse event related to the treatment under investigation has occurred.
2. A significant evidence of benefit

8.5.1 Purpose of Interim Analyses

An interim analysis will be performed because of uncertainty about the safety of the PCT-guided treatment strategy. Subjects who will not receive antibiotic therapy in the presence of a bacterial infection (because of a false-low/negative PCT concentration) could deteriorate because of the withholding of antibiotic treatment. This could lead to adverse outcomes, such as longer duration of hospital stay, ICU admission or death.

Another reason for performing the interim analyses is the possibility of a significant evidence of benefit of the PCT-guided treatment strategy according antibiotic treatment. A significant reduction in treatment failure could also mean a significant reduction in ICU admission, need for non-invasive ventilation, readmission, re-exacerbation and death.

8.5.2 Planned Schedule of Interim Analyses

An interim analysis will be performed at 50% of patient accrual, analysing the primary outcome and safety data. The safety data consists of observed adverse events and SAE. A DSMB will assess this interim analysis.

8.5.3 Stopping Rules

Criteria on which the DSMB may decide to terminate the trial prematurely are:

1. Any serious adverse event related to the treatment under investigation has occurred.
2. A significant evidence of benefit

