#### **9.5 [Data Safety Monitoring Board (DSMB) / Safety Committee]**

An interim analysis will be performed at 50% of patient accrual, analysing the primary outcome and safety data. The safety data consists of observed adverse events and SAE. A DSMB will assess this interim analysis. The members of the DSMB will be dr. [name] (pulmonologist Franciscus Gasthuis & Vlietland), dr. [name] (medical microbiologist Erasmus Medical Center) and prof. dr. ir. [name] (Professor of Clinical Epidemiology of Cardiovascular Diseases Erasmus Medical Center). The advice(s) of the DSMB will only be sent to the principal investigator of the study. Should the principal investigator decide not to fully implement the advice of the DSMB, the principal investigator will send the advice to the reviewing Ethical Committee (in Dutch: METC), including a note to substantiate why (part of) the advice of the DSMB will not be followed.

Criteria on which the DSMB may decide to terminate the trial prematurely are:

1. Any serious adverse event related to the treatment under investigation has occurred.
2. A significant evidence of benefit

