#### **10.4 Interim analysis (if applicable)**

An interim analysis will be performed after 50% of the participants needed has been accrued/included. The analysis will focus on the primary outcome and on safety. The non-inferiority design of the study means that a clear disadvantage of the PCT-guided treatment arm or in other words a clear benefit of the usual care arm will lead to discontinuation of the trial. The p-value at the interim analysis will be 0.0054 according to the O'Brien-Fleming method, and the p-value at final analysis will be 0.0492 (27). The safety data consists of observed adverse events and SAE. The change of the p-value at final analysis will lead to an increase of 2 patients per treatment arm. The number of patients per treatment arm will be 315. Using a 10% drop-out rate this will lead to a total number of patients of 693.

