In international literature there is scarce information about the percentages of treatment failure in patients admitted with an AECOPD receiving usual care. Therefore, we have performed a further search on PCT studies with a primary outcome of 30-day treatment failure. In the study by Schuetz et al. [6], who studied patients with lower respiratory tract infection, 30-day treatment failure was observed in 15.5% of the patients randomised to biomarker-based treatment, as compared to 18.9% in those randomised to usual care. This implies a relative risk of 0.82 in favour of the biomarker-based strategy. The study by Schuetz et al. was designed as a non-inferiority study, using a non-inferiority boundary of 7.5%. In view of these data we decided to design our study as a non-inferior study, whereas we choose a non-inferiority boundary of 5.0%. We based the primary outcome on the study of Huang et al. [13]. The incidence of the primary outcome was 20.4%. Using the relative risk of 0.82 in favour of the PCT-guided treatment group we expect the incidence of the primary outcome to be 16.7% in the PCT-guided treatment group. Then a total sample size of 626 is required (313 per treatment arm) to demonstrate non-inferiority with a power of 80%, and applying a one-sided alpha error of 0.025. We aim to enroll a total of 690 patients, accounting for a 10% drop-out rate.

8 General Analysis Considerations

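### The DSMB stopping list leaves out the between-arm harm criterion that Protocol 10.4 and SAP 8.5.5 say will end the trial, and the one interim p-value has no stated side or direction

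*SAP*

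**What the plan says.** Two sets of statements govern the interim look at 50% of accrual.

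- **The list.** Protocol 9.5, SAP 8.5 and SAP 8.5.3 (headed as the stopping rules) give two criteria on which the DSMB *may* terminate: "Any serious adverse event related to the treatment under investigation has occurred" and "A significant evidence of benefit".
- **The text on adjustment.** Protocol 10.4 and SAP 8.5.5 say that a clear disadvantage of the PCT-guided arm, put another way as "a clear benefit of the usual care arm will lead to discontinuation of the trial", is what ends the trial. This text is mandatory and does not mention stopping for benefit of the PCT arm. The next sentence gives the interim p-value as 0.0054 and the final one as 0.0492.

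SAP 8.5.1 gives the purpose: "An interim analysis will be performed because of uncertainty about the safety of the PCT-guided treatment strategy". It describes the feared harm as deterioration in patients with a bacterial infection and a falsely low PCT who go without antibiotics. It then adds possible benefit as another reason.

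Neither document says whether 0.0054 is one- or two-sided, whether it applies to harm, benefit or non-inferiority, or what makes a disadvantage clear.

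**The concern.** The look exists first of all to detect harm from withholding antibiotics, yet the list under the stopping-rules heading has no criterion that compares the arms for harm. Its safety criterion has no count, rate or comparison. One drug reaction in either arm meets it, while a surplus of readmissions or pneumonias in the PCT arm may not, if those events are not judged related to treatment. A DSMB member who reads the list and one who reads 10.4/8.5.5 would hold different rules, one optional and one mandatory.

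A second, separate question is what happens if 0.0054 is taken as the harm boundary, as its position in the text invites. A strict value at half the sample can pass over harm well above the 5-point margin.

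**Working it through.** **Inputs.** SAP section 7 and Protocol 4.4: 20.4% failure in usual care, 16.7% expected in the PCT arm, 5-point margin, 80% power, one-sided 0.025. Protocol 10.4 and SAP 8.5.5: 0.0054, 0.0492, 315 per arm, 693 in total. Half of 315 is about 157 per arm; half of 693 is about 173 per arm.

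**Step 1, the plan's own figures.** n per arm = (z_α + z_β)² × [p_C(1−p_C) + p_T(1−p_T)] / (margin + p_C − p_T)².
- One-sided 0.025: (1.960 + 0.842)² × (0.1624 + 0.1391) / 0.087² = 312.6, so 313.
- One-sided 0.0246 (half of 0.0492): (1.967 + 0.842)² × 0.3015 / 0.087² = 314.2, so 315.

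Both match the plan. The final value 0.0492 is therefore two-sided, and I take its partner 0.0054 as two-sided too (z = 2.78). The documents do not say so.

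**Step 2, the excess needed.** For an observed difference d, solve d / √{[0.204×0.796 + (0.204+d)(0.796−d)]/n} = 2.78. This gives d = 13.8 points at n = 157 and 13.1 at n = 173. With a pooled variance the values are 14.0 and 13.3.

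**Step 3, the chance of crossing.** P = Φ(Δ/SE − z), with SE from the two true rates. Example at n = 157, Δ = 10 points: SE = √[(0.1624 + 0.2116)/157] = 0.0488; 0.10/0.0488 − 2.782 = −0.73; Φ = 23%. The true excesses are my assumptions, since the documents give none. Ranges run over n = 157 to 173.

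| True excess in PCT arm | two-sided 0.0054 | one-sided 0.0054 | one-sided 0.025 |
|---|---|---|---|
| −3.7 points (design) | <0.1% | <0.1% | 0.22-0.25% |
| 0 | 0.3% | 0.5% | 2.5% |
| +2 | 1% | 2% | 6-7% |
| +4 | 3% | 4-5% | 13-14% |
| +5 (margin) | 4-5% | 7% | 18-20% |
| +10 | 23-26% | 31-35% | 54-58% |
| +15 | 59-65% | 68-73% | 85-88% |
| +20 | 88-91% | 92-94% | 98-99% |

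A pooled-variance test lowers the first column by at most about 2 points (57-63% at +15, 86-90% at +20). Binomial simulation agrees with that version to within about 1 point.

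**Step 4, the SAE criterion.** The chance of at least one related SAE among n patients is 1 − (1 − r)^n. The documents give no rate, so r is an assumption. The lower end of each range is 157 exposed patients and the upper end all 346 at the interim. For r = 0.1%, 0.5%, 1% and 2% the chance is 15-29%, 55-82%, 79-97% and 96-100%. None of these depends on whether the strategies differ.

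**The case against.** The two texts do not forbid what the other requires. The list says when the DSMB *may* stop, and 10.4/8.5.5 add a case in which stopping *will* follow. The harm rule stands in the same SAP section, two subsections after the list, and the DSMB receives the primary outcome and all safety data. Nothing says that the DSMB must work from 8.5.3 to the exclusion of 8.5.5, or that it must use 0.0054 for harm; it may judge for itself what is clear. Protocol 5.1 counts no antibiotic therapy as part of the investigational treatment, and Protocol 9.2.2 makes death and hospitalization SAEs. A death or readmission attributed to withheld antibiotics could therefore meet the first listed criterion.

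Most of this stands, and it rules out several stronger readings that a reader might infer:

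- *The plan has no harm rule.* It has one, but not in the list.
- *The look has almost no sensitivity to harm.* This is fair near the margin only. True excesses of 15 to 20 points would be caught 59-91% of the time.
- *The omission causes the low sensitivity.* It does not. That comes from using 0.0054 at half the sample and would be the same if the list named harm.
- *0.0054 is the benefit boundary.* The documents do not support that. It directly follows the harm sentence, in text that does not mention stopping for benefit.

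The objection does not remove the mismatch. The list is incomplete for the first purpose of the look, its SAE criterion is ambiguous on relatedness and does not compare arms, and the key terms are undefined.

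**Conclusion.** The point holds as an inconsistency in the stopping rules that should be corrected. An optional list naming benefit and any related SAE stands beside a mandatory rule naming only harm, and nothing ranks the two.

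The size depends on how 0.0054 is used. As a two-sided harm boundary it has low sensitivity up to about twice the margin (4-5% at +5 points, 23-26% at +10) and moderate to high sensitivity beyond that. Read as one-sided, it still catches a 10-point excess only 31-35% of the time.

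These figures assume 20.4% failure in usual care, a test against no difference, and 157 to 173 evaluable patients per arm. The main population is per-protocol (SAP 8.5.4), and its interim size is unknown. A smaller one would lower the chance of detecting a given harm.

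**What to change.** Reconcile Protocol 9.5 and SAP 8.5/8.5.3 with Protocol 10.4 and SAP 8.5.5 into one list, used in both documents and by the DSMB:

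1. Carry over the between-arm harm criterion on the primary outcome that 10.4/8.5.5 already state, and say whether it is mandatory or advisory.
2. Replace the any-related-SAE criterion with DSMB review of SAEs compared by arm, whatever their judged relatedness.
3. State the side of 0.0054 and what it governs, and define a clear disadvantage. Only the sponsor can say what was meant.

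This costs an amendment to wording in the protocol, the SAP and any DSMB instructions. It changes no sample size.

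As an option for the sponsor and DSMB, harm could have its own less strict, non-binding threshold. Stopping for harm cannot add a false conclusion of non-inferiority, so type I error is not inflated. One-sided 0.025, as an illustration, would be crossed 54-58% of the time at +10 points. The price is some stops that might not be wanted: about 0.25% under the design assumption, 2.5% under equality, and about 6-14% for true excesses of 2 to 4 points, which lie inside the margin. In that last range the practical loss is limited: by the formula in Step 1, final power at 315 per arm is only about 15% at +2 points, 9% at +3 and 5% at +4.

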8.5.4 Analysis Methods to Minimize Bias

The per protocol (PP) population is the main analysis population because of the non-inferiority design of the trial.

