8.2.2 Per Protocol Population

- All subjects who:
 - met all inclusion/exclusion criteria,
 - attained a sufficient compliance to the treatment received, treatment with prednisolone and/or antibiotics, when prescribed on admission for at least 5 days,
 - did not present serious deviations from the protocol.

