8.2.3 Safety Population

- All subjects who received any study treatment (including control) but excluding subjects who drop out prior to receiving any treatment.

The analysis of all the efficacy variables will be performed on both the ITT and the PP populations in order to assess the robustness of the findings from the ITT population.

All the demographic and baseline patients' characteristics and safety outcomes will be analysed using the ITT population.

All efficacy variables will be analysed for ITT and the PPS, and the PP population will be considered the primary population for assessing efficacy.

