9.3 Protocol Deviations

When a physician decides to prescribe antibiotic therapy even though the patient has a low serum concentration of procalcitonin ($\leq 0.25 \mu\text{g/mL}$) this leads to a protocol violation. The patient might recover because of the antibiotic therapy instead of still experiencing symptoms on day 30, which could directly impact the primary endpoint. This subject should not be analyzed in the per protocol analysis, because of this major protocol deviation/violation.

Early termination of antibiotic therapy, in both groups, could have an impact on the primary endpoint. This could happen when a patient has an initial quick recovery and gets discharged from the hospital without antibiotic therapy and then has a relapse. We do not expect this to happen more in one of the two treatment arms, although a high PCT might lead to less frequent discontinuation of the treatment when the patient is discharged in the first 5 days (the antibiotic therapy should be given during 5 days in both groups).

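### The interim section names per protocol as the main population, so the primary-outcome comparison behind the harm stop would be led by a set that does not preserve randomisation

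*SAP*

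**What the plan says.** SAP 8.5.1 gives the first reason for the look: "An interim analysis will be performed because of uncertainty about the safety of the PCT-guided treatment strategy". It describes patients with a falsely low PCT who "could deteriorate because of the withholding of antibiotic treatment". SAP 8.5.2 sets timing and content: "An interim analysis will be performed at 50% of patient accrual, analysing the primary outcome and safety data". SAP 8.5.5 says a clear disadvantage of the PCT arm ends the trial, and then gives p-values of 0.0054 (interim) and 0.0492 (final).

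The only analysis population named in section 8.5 is in 8.5.4: "The per protocol (PP) population is the main analysis population because of the non-inferiority design of the trial".

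Three other places determine what that means:

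- SAP 8.2.2 defines PP by eligibility, absence of serious deviations, and compliance with "treatment with prednisolone and/or antibiotics, when prescribed on admission for at least 5 days".
- SAP 9.3 adds an exclusion that can arise only in the PCT arm: "When a physician decides to prescribe antibiotic therapy even though the patient has a low serum concentration of procalcitonin", a violation has occurred, and "This subject should not be analyzed in the per protocol analysis, because of this major protocol deviation/violation". No time limit is given.
- SAP 8.2.3 gives the general rule on safety: "All the demographic and baseline patients' characteristics and safety outcomes will be analysed using the ITT population". It also has efficacy variables analysed on both ITT and PP, with PP primary. Protocol section 10 agrees.

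**The concern.** PP is often chosen for a non-inferiority conclusion because protocol departures in an ITT analysis can make two arms look alike. That reasoning does not carry over to a harm comparison. The DSMB has to ask whether patients allocated to the PCT strategy fare worse than those allocated to usual care, and a physician overruling a low PCT is part of how that strategy plays out.

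The SAP 9.3 exclusion acts after randomisation and in one arm only. In usual care, antibiotics are the physician's choice (Protocol section 5), so there is no counterpart to remove. If overruled patients differ in prognosis from the rest of their arm, removing them shifts the PCT-arm failure rate while usual care has no corresponding removal. Treatment failure is the outcome the interim threshold applies to, so the shift would act on the DSMB's one formal comparison.

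**Working it through.** **The plan's own figures.** With failure rates of 20.4% and 16.7% and a 5-point margin (SAP section 7):

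n per arm = [0.204 × 0.796 + 0.167 × 0.833] × (1.960 + 0.842)² / (0.05 + 0.037)² = 312.6, so 313.

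At one-sided 0.0246 (half of 0.0492) the result is 314.2, so 315, and 630 × 1.10 = 693. All three figures reproduce, and the sample size is not in question. The match at 0.0246 indicates that 0.0492 is two-sided. I read 0.0054 the same way (z = 2.78).

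**Illustration of the bias.** The usual-care rate of 20.4% is from the SAP. The following are assumptions, because the documents do not give them:

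- a true PCT-arm rate of 30.4% (a 10-point excess);
- a share x of the PCT arm removed, 5% or 10%;
- a failure rate f among those removed, from 20.4% to 70%;
- no removals from usual care.

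The look has 157 per arm (half of 315).

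PP rate in the PCT arm = (0.304 − x·f) / (1 − x)

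Chance of crossing = Φ(difference / SE − 2.78), with unpooled SE and 157(1 − x) against 157 patients.

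All randomised: SE = √(0.304 × 0.696/157 + 0.204 × 0.796/157) = 0.0488, so Φ(0.100/0.0488 − 2.78) = 23%.

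| Removed (x) | Failing among removed (f) | PP rate, PCT arm | PP excess (points) | Chance of crossing 0.0054 |
|---|---|---|---|---|
| 5% | 20.4% | 30.9% | 10.5 | 25% |
| 5% | 30.4% | 30.4% | 10.0 | 22% |
| 5% | 50% | 29.4% | 9.0 | 17% |
| 5% | 70% | 28.3% | 7.9 | 12% |
| 10% | 20.4% | 31.5% | 11.1 | 28% |
| 10% | 30.4% | 30.4% | 10.0 | 21% |
| 10% | 50% | 28.2% | 7.8 | 11% |
| 10% | 70% | 26.0% | 5.6 | 5% |

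Example: (0.304 − 0.10 × 0.70)/0.90 = 0.260, and 0.260 − 0.204 = 0.056.

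With 173 per arm (693/4), the all-randomised chance is 26%. For x = 5%, f = 50% it is 19%, and for x = 10%, f = 70% it is 6%.

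The sign turns on f. Above the arm's own rate of 30.4%, PP understates the harm; below it, PP overstates it; at 30.4% the excess is unchanged and only some precision is lost.

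**Who SAP 9.3 removes.** SAP 5.2 lists an antibiotic start after an initial opposite decision (after 48 hours) as a secondary endpoint. Table 2 reports it by arm, and SAP sections 9 and 17 put Table 2 on the PP population. If 9.3 removed every low-PCT patient who started antibiotics later, the PCT-arm cell would contain none of them. That suggests 9.3 may cover only overrides at the initial treatment decision, but the text does not say so.

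**The case against.** The strongest reply is that the plan already protects the safety review. SAP 8.2.3 puts safety outcomes on ITT, and the interim covers adverse events and SAEs separately from the primary outcome. Mortality, pneumonia, readmission and ICU admission appear in the SAP's safety table, so many serious failures would reach the DSMB there. The stopping criterion on treatment-related SAEs is not tied to PP. Efficacy variables are to be analysed on ITT as well, and 8.5.4 may only repeat the trial-wide rule. All of this stands, and it limits the point to the primary-outcome comparison. It does not settle that comparison: 8.2.3 makes PP primary for efficacy variables, 8.5.4 repeats PP inside the interim section, and nothing says ITT governs the harm stop.

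A reader might infer that PP strips out the deteriorating PCT-arm patients the look is meant to find. The documents do not support that. Low-PCT patients who fail without antibiotics stay in PP, as do high-PCT patients treated as assigned, and Table 2 suggests that later starts may stay in too.

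A reader might also infer that PP must hide harm. SAP 9.3 itself worries about the reverse, that an overruled patient recovers because of the antibiotic. If so, removal would raise the apparent excess. The PP criteria in 8.2.2 also apply to both arms, and the illustration ignores removals from usual care.

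Last, a reader might think PP drops patients who need ICU care or non-invasive ventilation within 72 hours. That criterion applies to both arms, neither event is a component of the primary endpoint, and the SAP does not say that a later event undoes eligibility.

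**Conclusion.** The point holds for the interim comparison of the primary outcome. As written, it would be led by a set defined partly by decisions after randomisation, with one exclusion that can occur only in the PCT arm, although the stated purpose is to detect harm from that arm's strategy. The comparison can therefore be biased.

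The size is not known. For an assumed 10-point excess and 5% to 10% removed, PP would show 9.0 to 5.6 points if 50% to 70% of those removed fail, and 10.5 to 11.1 points if 20.4% fail. The chance of crossing, 23% in all randomised patients, becomes 17% to 5% in the first case and 25% to 28% in the second. The case for change rests on the lost randomisation and not on any one of these figures.

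The adverse-event stream and the choice of PP for the final non-inferiority conclusion are outside this finding.

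**What to change.** In SAP 8.5.4, state that the interim harm comparison of the primary outcome, and the interim safety data, use all randomised patients as allocated, with PP supportive. Keep PP as primary for the final non-inferiority analysis.

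Write all randomised patients rather than ITT. SAP 8.2.1 requires at least one dose of study drug and does not define that term. If it means the antibiotic, low-PCT patients who received none would drop out of that set; if it includes prednisolone, which Protocol section 5 gives to every patient, they would not.

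In SAP 9.3, state whether an antibiotic start after an initial decision to withhold counts as the deviation, and make this agree with the Table 2 row on later starts.

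The cost is two or three sentences. The data are already collected, and the sample size does not change.
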